#### **12.4.2 Visits 2-9 (Treatment Visits)(+/- 6 days)**

These visits are for weeks 4, 8, 12, 16, 20, 24, 28 and 32. The following procedures will be done at these visits:

- Vital signs (pulse, blood pressure) and weight will be taken and recorded.
- The subject will complete the PHQ9 mood questionnaire
- Complete physical exam including and testicular examination and volume measurement will be performed.
- Subjects will be questioned regarding concomitant medications and adverse events.
- Any unused study drug counted for drug accountability and returned to subject? At treatment visit 32 or early exit visit, all unused study drug will be collected.
- Study drug log will be reviewed to check the date and time of drug administration. These logs will be collected at each treatment visit.
- A blood sample will be drawn at week 8, 16, 24 and 32. The time of day of the blood draws will be recorded in the source document.
- A semen sample will be obtained for the presence of sperm, and, if present, the measurement of sperm count, concentration, motility and morphology
- Fasting blood samples will be obtained for the following measurements: CBC, clinical chemistry including glucose, liver and renal function tests (urea, creatinine, albumin, calcium, alanine aminotransferase, aspartate aminotransferase, gamma glutamine transferase, alkaline phosphatase, bilirubin, and albumin), creatine kinase, full lipid panel including total cholesterol, HDL and LDL, triglycerides, hematology (hematocrit, hemoglobin), and testosterone, FSH and LH at weeks 8, 16, 24, and 32.
- In addition, blood samples will be collected at each visit for two serum samples to be frozen for the future analysis of serum retinoid levels.
- Subjects will be scheduled to return to the clinic for follow-up visits.
- Subjects will be given the next month's supply of study drug at visits 2-8 (weeks 4, 8, 12, 16, 20, 24 and 28).

### **12.4.3 Visit 10 and 11 (Follow-up Visits) +/- 6 days**

These visits are for weeks 44 and 56. The following will be done at these visits:

- Vital signs (pulse, blood pressure and respiratory rate) will be taken and recorded.
- The subject will complete the mood (PHQ-9) questionnaire.
- Subjects will be questioned regarding concomitant medications and adverse events.
- Fasting blood samples (week 56 only) will be obtained for the following measurements: CBC, clinical chemistry including glucose, liver and renal function tests (urea, creatinine, albumin, calcium, alanine aminotransferase, aspartate aminotransferase, gamma glutamine transferase, alkaline phosphatase, bilirubin, and albumin), creatine kinase, full lipid panel including total cholesterol, HDL and LDL, triglycerides, hematology (hematocrit, hemoglobin), and testosterone, FSH and LH. In addition, two serum samples will be frozen for the future analysis of serum retinoid levels.
- A semen sample will be obtained to ascertain the presence of sperm, and, if present, the measurement of sperm count, concentration, motility and morphology

### **13. Study Withdrawals**

Subjects withdrawn from the study can be replaced only if the withdrawal occurs before the start of the treatment. Subjects who have had study drug will not be replaced, regardless of the reason for discontinuation. All efforts will be made to contact any subject who decides to discontinue study participation before the end of study safety procedures (Visit 11). The necessary clinical and laboratory examinations planned at the last visit should be performed at the end of the study whenever it occurs. The reasons for discontinuation will be documented.

#### **Post-Admission Withdrawal Criteria**

Subjects may be discontinued prematurely for any of the following reasons:

- Emergence of a severe condition(s) such that, in the judgment of the investigator, continuation in the trial would negatively impact the health of the subject.
- Personal reasons (*e.g.* withdrawn consent).
- Non-compliance with study drug

- Subject lost to follow-up
- A severe skin reaction judged by the investigator to potentially be related to the study drug
- A persistent elevation of serum triglycerides
- Onset of neutropenia
- New onset of hearing disorder
- New onset of visual changes
- Onset of abdominal pain, rectal bleeding or severe diarrhea
- Persistent, significant increase of liver enzymes or bilirubin
- New onset of significant serum glucose elevation
- New onset of headache associated with nausea and vomiting
- Persistent elevation of serum calcium
- Development of kidney stones
- Increase in the PHQ9 score to >15 (suggestive of moderately severe depression)

## 14. Statistical Considerations

**Data analysis and Interpretation of Results:** The primary endpoint is the presence of sperm in the ejaculate at week 32 of treatment compared with its absence at baseline. The presence of sperm after 32 weeks of treatment will be compared with baseline using a Wilcoxon sign-rank test. Linear regression will be performed to determine if significant relationships between baseline (or delta) serum concentrations of 13-cis retinoic acid and changes in sperm quality are present using STATA Version 10.0 (College Park, TX, USA). For all comparisons, an alpha of 0.05 will be considered significant.

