Study Design	
We will conduct an unblinded, pilot study to determine the impact of therapy with 13-cis retinoic acid on sperm indices in azoospermic men. Twenty azoospermic men, ages 21-60 will be enrolled in a 32-week study of 20 mg twice daily of 13-cis retinoic acid. The subjects will be closely followed for side effects related to treatment. The impact of treatment on the appearance of sperm in the ejaculate will be determined by monthly seminal fluid analyses.
 
All aspects of this study will be performed in compliance with Good Clinical Practice (GCP) regulations, ICH guidelines, the Declaration of Helsinki, and under an FDA Investigational New Drug (IND) application.

Number of Subjects	Twenty men.
Duration of Trial	Enrollment should be completed in about 18 months, resulting in total study duration of about 36 months including screening, treatment phase, end of study visit procedures, close out and data analysis.
Duration of Treatment	The active treatment phase will be 32 weeks.
Dosage and Regimen	13- cis retinoic acid at 20 mg twice daily with meals for 32 weeks.
Inclusion Criteria	Subjects will be infertile men with azoospermia on at least two semen analyses separated by at least one week and no pregnancy with partner with normal cycles and normal hysterosalpingogram despite >1 year of unprotected intercourse.
Exclusion Criteria	Exclusion criteria include: hypogonadotropic hypogonadism (that might respond to gonadotropin injections), the use of anabolic steroids, illicit drugs, or the consumption of more than 4 alcoholic beverages daily, severe mental health problems, or current therapy with retinoic acid (e.g. Accutane) or vitamin A.
Efficacy Parameters	The appearance of sperm in the ejaculate during treatment
Safety Parameters	
 
• CBC, clinical chemistry panel (glucose, liver and renal function tests including urea, creatinine, albumin, calcium alanine aminotransferase, aspartate aminotransferase, alkaline phosphatase, bilirubin), CK, full lipid panel
 

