	
including: Total cholesterol, HDL, LDL and fasting triglycerides at baseline, week 8, 16, 24 and 32 of treatment, and study exit. Additional measures will be conducted if any abnormal values are found until the end of study visit.
 
 
• Adverse event and concomitant medications throughout the study. Other safety parameters include vital signs; and changes in pre- and post-treatment physical examination results and score on the PHQ9 depression questionnaire.
 

Evaluations	
The following determinations will be made in all subjects:
 
 
• Semen analysis will be collected twice during screening and every four weeks during treatment and twice during recovery
 
• Serum samples will be collected for the measurement of: vitamin A, all-trans and 13-cis retinoic acid, testosterone, FSH and LH. Serum for these measures will be collected before the beginning of the treatment, and every two months during treatment and sy study exit.
 

Other Assessments	
Demographic characteristics, including age and race, will be collected.

Statistical Analysis	
The primary endpoint is the appearance of sperm in the ejaculate of treated men between baseline and 32 weeks. This analysis will be conducted using a Wilcoxon signed-rank test.

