### **12.2 Laboratory Samples**

Blood samples for laboratory analyses will be collected at the first screening visit, and at the treatment visits on weeks 8, 16, 24, 32 and 56 with the subject in a fasting state (no food or drink other than 4 to 6 ounces of water or non-sweetened clear liquids for a minimum of 8 hours). A snack will be provided after the blood is drawn. If the subject is in a non-fasting state, the investigator will reschedule the visit within two days. The investigator will review all laboratory reports and file a copy with each subject's chart and CRFs. The CBC and blood chemistry samples will be analysed at the local hospital laboratory at the University of Washington.

The serum samples for measurements of retinoic acid will be frozen for analysis at the end of study. In terms of processing, the blood samples will be collected into vacutainers (containing serum separating tube gel and clot activator) wrapped aluminum foil to prevent light exposure that can degrade retinoic acid, and gently mixed. The samples will be allowed to clot for 30 minutes at room temperature before centrifugation at 1000-2000g for 15 minutes. Following centrifugation, the serum samples will be frozen in (light protection?) tubes at -80 C.

**Semen Analysis:** Semen will be collected after at least 48 hours of abstinence from ejaculation at the two screening visits, treatment visits 2-9, and all follow up visits. The semen will be assessed for the presence of sperm, and, if present, for count and motility. In addition, a known volume of semen will be diluted and washed for making smears for morphology assessments. These

procedures allow for accurate total sperm count and motility assessments following the WHO protocol (18).

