### 14.1 Sample size consideration

Inclusion of 20 men will allow for an 80% power to detect a response rate of greater than 15% in terms of sperm production and allow for a drop-out rate of 10% at an alpha of 0.05 (The primary outcome).

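### The planned signed-rank test neither tests nor estimates the response rate the trial is sized on, and no version of it exceeds 60% power at a true 15% rate, against the 80% stated.

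*Combined protocol and SAP*

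**What the plan says.** Section 14 defines the primary endpoint as sperm being present at week 32 when there was none at baseline, and gives the analysis as: "The presence of sperm after 32 weeks of treatment will be compared with baseline using a Wilcoxon sign-rank test". The Synopsis repeats it: "This analysis will be conducted using a Wilcoxon signed-rank test". The only further detail is "For all comparisons, an alpha of 0.05 will be considered significant". Stata 10.0 is named in the same paragraph, but for the regression.

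Section 14.1 justifies the sample size on a different basis: "Inclusion of 20 men will allow for an 80% power to detect a response rate of greater than 15% in terms of sperm production". The same number is to "allow for a drop-out rate of 10% at an alpha of 0.05".

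Four other places bear on this:

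- Section 9.1.1, criterion 2, requires azoospermia on two semen analyses, so every baseline is zero.
- Section 12.2 collects both a yes/no result and counts: "The semen will be assessed for the presence of sperm, and, if present, for count and motility".
- Section 13 does not allow replacement of men who have taken study drug.
- The Synopsis words the endpoint window in two further ways: "The appearance of sperm in the ejaculate during treatment" under Efficacy Parameters, and "The primary endpoint is the appearance of sperm in the ejaculate of treated men between baseline and 32 weeks" under Statistical Analysis.

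No section plans a responder proportion or a confidence interval. CI appears only in the list of abbreviations.

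**The concern.** The signed-rank test asks whether within-man changes are symmetric about zero. Here eligibility rules out a negative change. All non-zero changes are positive, and the test compares the responders with a 50:50 split of signs. The men who did not respond contribute little or nothing. The test therefore does not address the response rate on which the trial is sized.

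Section 14.1 can be read in two ways. In reading A, the trial has 80% power when the true rate is 15%. In reading B, 15% is the rate to be exceeded, in which case no alternative rate is given.

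Three things are at stake. Enrolment is 20 and treated men are not replaced, so a power shortfall cannot be made up and a real signal may be reported as non-significant. The unstated choices leave significance open at responder counts that are quite likely to occur. And the main thing a pilot can deliver, the share of men who respond with its uncertainty, has no planned estimate.

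**Working it through.** **Inputs.** 20 men, 10% dropout, alpha 0.05, response rate 15% and power 80% (Section 14.1); all baselines zero (Section 9.1.1). Evaluable men: 20, or 20 × 0.9 = 18.

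**The plan's own figure.** At a true 15% rate, P(at least 2 responders) is 82.4% with 20 men and 77.6% with 18. P(at least 3) is 59.5% and 52.0%. A power near 80% therefore needs significance at 2 responders.

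**Can 2 responders be significant?** Let k men respond, with ranks r for their changes.

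- Exact: p = 0.5^k one-sided, 2 × 0.5^k two-sided. At k = 2 these are 0.25 and 0.50.
- Large-sample: all signs are positive, so z = Σr / √(Σr²), which cannot exceed √k for any ranks; 0/1 data give equality. At k = 2, z is at most 1.414 and the smallest one-sided p is 0.0786.

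So no version is significant at 2 responders. At least 3 are needed, and 59.5% (20 men) or 52.0% (18 men) is a ceiling however ties, zeros and sidedness are handled.

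**Power by version at a true 15% rate**, as P(X ≥ c) for X binomial:

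| Version | Responders needed (p there) | 20 men | 18 men |
|---|---|---|---|
| One-sided large-sample, 0/1 data | 3 (0.042) | 59.5% | 52.0% |
| One-sided large-sample, untied counts, zeros dropped | 4 (0.034) | 35.2% | 28.0% |
| Two-sided large-sample, 0/1 data | 4 (0.046) | 35.2% | 28.0% |
| Two-sided large-sample, untied counts, zeros dropped | 5 (0.043) | 17.0% | 12.1% |
| One-sided exact | 5 (0.031) | 17.0% | 12.1% |
| Two-sided exact | 6 (0.031) | 6.7% | 4.2% |

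Untied counts with the zeros ranked have the same cut-offs as 0/1 data. The true rate needed for 80% power is 20% (20 men) or 22% (18 men) for the most lenient version, and 37% or 40% for the two-sided exact version. At a true 15% rate, 80% power needs 28 evaluable men with a cut-off of 3, and 52 with a cut-off of 6.

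**Other routes to 80%.** McNemar needs 50 men two-sided or 39 one-sided; a Wald test needs 45 or 36. The one near match is a one-sided arcsine formula for two independent groups of 20 (80.8%), which does not fit a single-arm paired design and gives 77.1% with 18.

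**Disagreement between versions.** At 4 and 5 responders the two-sided exact p is 0.125 and 0.0625; the large-sample p on 0/1 data is 0.046 and 0.025. At a true 15% rate, P(4 or 5 responders) is 28% with 20 men and 24% with 18. If one-sided testing is also open, versions disagree at 3 to 5 responders: 53% and 48%.

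**Reading B.** Used as a test against 15%, the signed-rank test would reject at a true rate of exactly 15% in 7% to 60% of trials of 20 men (the 20-men column again). An exact binomial test against 15% needs 7 of 20 (size 0.022) and reaches 80% power only at a true rate of 42%, or 46% if two men count as non-responders.

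**The case against.** The strongest objection is that the low power comes mainly from having 20 men and a 15% rate, not from the test. An exact binomial test with the same 20 men has 60% power (52% with two men counted as non-responders) against an assumed 2% or 4% background, and 35% (28%) against 5%. These equal the large-sample signed-rank figures on 0/1 data. This stands: changing the test does not by itself restore 80%. What cures the defect is a planned estimate with its interval and a corrected power statement.

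Second, the sentence says greater than 15%, and the true rate might be higher. At 20% the most lenient version has 79.4% power with 20 men. That needs a one-sided, uncorrected large-sample test and no dropout; with 18 men it is 72.9%. The plan names no such rate.

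Third, because the result depends on the responder count, the test does indirectly address whether the rate is above zero. That is fair. It still does not test against 15% or any other stated rate.

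Fourth, the 28% disagreement figure holds for 0/1 data or ranked zeros. With untied counts and zeros dropped, the two-sided versions differ only at 5 responders (10% with 20 men, 8% with 18). This is correct, and the plan does not say which applies.

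Last, this is an unblinded pilot with no go/no-go rule tied to the p-value. But it makes a formal power claim, and this is its only primary analysis.

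**Conclusion.** The concern holds and should be fixed before analysis. The test does not match the response-rate basis of the sample size, and it provides no estimate. Read as power at a true 15% rate, the stated 80% is not reachable: the range is 6.7% to 59.5% with all 20 men and 4.2% to 52.0% with 18. The 59.5% ceiling is a mathematical bound over versions of the test, and assumes only zero baselines, independent men and a true 15% rate. Read as a test against 15%, the plan states no alternative rate and names a test that does not address that null. The disagreement figures depend on which version is run, which the plan leaves open.

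**What to change.** 1. Settle the endpoint window first: week 32 only (Section 14), during treatment (Synopsis, Efficacy Parameters), or from baseline to 32 weeks (Synopsis, Statistical Analysis). Which samples qualify depends on this.
2. In Section 14 and the Synopsis, make the primary analysis the proportion of men with sperm in that window among all men who took study drug, with an exact (Clopper-Pearson) 95% confidence interval. Count men without a qualifying sample as non-responders. A completers-only denominator raises the rate (3/18 = 16.7% against 3/20 = 15%), so report it as a sensitivity analysis.
3. Drop the signed-rank test, or keep it only to describe sperm counts.
4. A test is optional. If one is kept, use an exact one-sample binomial test with the background rate and sidedness stated and justified by the sponsor in advance.
5. In Section 14.1, say whether 15% is the null or the alternative, and replace the 80% sentence with the interval precision or the power of the chosen analysis.

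Precision with 20 men: 0 responders, 0% to 16.8%; 3 responders, 3.2% to 37.9%; 5 responders, 8.7% to 49.1%.

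Power of the binomial test at a true 15% rate, denominator 20, one-sided 0.05, with no dropout / two men counted as non-responders:

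| Assumed background | Responders needed | Power |
|---|---|---|
| 1% | 2 | 82% / 78% |
| 2% | 3 | 60% / 52% |
| 4% | 3 | 60% / 52% |
| 5% | 4 | 35% / 28% |

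At 0.025 per tail only the 4% row changes, to 4 responders and 35% / 28%. The background rates are assumptions; the documents give none.

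The cost is wording in Section 14, Section 14.1 and the Synopsis, plus the justification of one background rate if a test is kept. No new data or visits are needed.

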## **9. Selection of Subjects**

### **9.1.1 Inclusion Criteria**

1. Subjects will be infertile men (no pregnancy with partner with normal cycles and normal hysterosalpingogram despite >1 year of unprotected intercourse).
2. Azoospermia (no sperm apparent in centrifuged semen) as assessed by semen analysis on two occasions separated by one week.
3. In the opinion of the investigator, is able to comply with the protocol, understand and sign an informed consent and HIPAA form.

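### Section 14 relates serum 13-cis retinoic acid to changes in sperm quality, but no man has a baseline motility or morphology value, and change in count will be zero for most men

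*Combined protocol and SAP*

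**What the plan says.** The regression sentence in section 14 (Statistical Considerations) covers relationships between "baseline (or delta) serum concentrations of 13-cis retinoic acid and changes in sperm quality are present". The same paragraph sets one threshold: "For all comparisons, an alpha of 0.05 will be considered significant". It does not define sperm quality, name the visit or the set of men, or say how a man without sperm enters the regression.

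Three other places fix what data can exist:

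- Section 9.1.1, criterion 2: "Azoospermia (no sperm apparent in centrifuged semen) as assessed by semen analysis on two occasions separated by one week".
- Section 12.2: "The semen will be assessed for the presence of sperm, and, if present, for count and motility".
- Section 12.4.2, for the treatment visits: a semen sample for the presence of sperm and, "if present, the measurement of sperm count, concentration, motility and morphology". Section 12.4.3 sets the same condition for the follow-up visits.

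The primary endpoint is a separate, binary matter: "The primary endpoint is the presence of sperm in the ejaculate at week 32 of treatment compared with its absence at baseline".

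**The concern.** Motility and morphology are proportions of the sperm present. With no sperm the denominator is zero, so there is no value, and no change can be taken from it. The analysis would suit men who start with some sperm, as in the earlier oligoasthenoteratozoospermia pilot described in section 1. It does not fit a trial whose entry rule is the absence of sperm.

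This is the only analysis in the plan that links drug exposure to outcome, and the rationale in section 3 rests on low intratesticular retinoic acid. Because the plan is silent, the analyst must choose after seeing the data: use count, restrict to men with sperm, or enter a number where no measurement exists. These choices answer different questions. Under the last, a relation between retinoid level and whether any sperm appear could be reported as a relation with the quality of the sperm.

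**Working it through.** **Plan's own figure.** The plan gives no figure for this regression, so there is none to reproduce. From section 14.1 I take only the planning response rate of 15% and the 10% drop-out. The 80% power stated there is not used.

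**1. What can be computed, by component** (taking week 32 as the on-treatment visit, as for the primary endpoint; section 14 names no visit for the regression)

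| Component | Baseline | Week 32, no sperm | Week 32, sperm | Change |
|---|---|---|---|---|
| Motility, morphology | no value | no value | measured | not computable for any man |
| Count, concentration | 0 | 0 | measured | computable; equals the week-32 value |

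**2. How many men have a zero change in count**

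- Evaluable men: 20 × (1 − 0.10) = 18.
- Expected without sperm at 15%: 18 × 0.85 = 15.3. Expected with sperm: 18 × 0.15 = 2.7.
- Range over assumed higher rates: 18 × 0.70 = 12.6 without sperm at 30%; 18 × 0.50 = 9 at 50%.

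**3. What happens if absent motility is entered as 0%** (an assumption; the plan does not say this)

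The change then equals motility × responder indicator. Simulation: n = 18; 20,000 trials per setting; standard normal retinoid level; logistic response; motility in responders uniform from 5% to 60% and independent of retinoid level; two-sided test at 0.05.

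| Response rate | Assumed log-odds per SD | Zero-coded regression significant |
|---|---|---|
| 15% | 1.0 | 20.6% |
| 15% | 1.5 | 33.5% |
| 30% | 1.0 | 27.9% |
| 30% | 1.5 | 46.1% |

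With no link between retinoid level and response, the rate is about 5%. A second simulation (8,000 trials per setting, motility mean 40 and SD 12) shows the same pattern. At log-odds 0, 1 and 2 it gives 4.8%, 22.7% and 51.2% at a 15% response rate, and 5.0%, 36.4% and 75.6% at 50%.

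The zero-coded change correlates with the responder indicator at a mean of 0.97 (15% response) or 0.92 to 0.93 (50%) in the second simulation. With the wider motility distribution of the first, the means are 0.93 (15%) and 0.88 (30%).

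**4. Restricting to men with sperm**

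The rejection rate stays at 4.8% to 5.2% when at least 3 men have sperm, the minimum for a slope test. At 15% and n = 18, the probability of 3 or more is 0.520, so a formal test often could not be run.

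**5. What a binary comparison can deliver**

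- P(0 responders) = 0.85^18 = 0.054.
- P(0 or 1 responder) = 1 − 0.776 = 0.224.
- With one responder among 18, the smallest two-sided exact rank-sum p is 2/18 = 0.11. With none there is no comparison.

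**The case against.** The strongest reply is that sperm quality is undefined and may mean count. Section 3 describes the aim as moving men from azoospermia to oligozoospermia, which is a count outcome, and section 5 speaks of indices of spermatogenesis. Baseline count is 0, so change in count exists for every man with a semen sample, and a regression on it can be run. This stands. A reader might infer that the planned regression is impossible for all 20 men; the documents support that only for motility and morphology. What remains is that the plan never limits quality to count, and that a mostly zero outcome fits linear regression badly.

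Second, zero-coding appears nowhere in the plan. That also stands, and the false-finding scenario is conditional on it. A reader might further take 21% to 46% as an inflated type I error rate. It is not. Those rates arise because the simulation assumes a real link with response (odds ratio about 2.7 or 4.5 per SD, sizes that no document supports). The zero-coded outcome is then truly associated with retinoid level, and the error would lie in calling the result sperm quality.

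Third, it is tempting to say that the regression retests the primary endpoint under another name. It does not. The primary analysis compares sperm presence with baseline; the regression asks whether retinoid level predicts outcome. They share the responder indicator but test different hypotheses.

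Fourth, Appendix 1 lists a semen analysis at T1, which section 12.2 omits. A man with sperm at T1 would have a pre-treatment value, but the plan does not name T1 as baseline.

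Finally, this is one sentence in a 20-man pilot, and sections 2.1 and 2.2 contain no objective on retinoid level. That limits the weight of the point without removing it.

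**Conclusion.** The point holds for motility and morphology: a change from screening cannot be computed for any man, because entry requires no sperm and both are measured only when sperm are present. This follows from the text and needs no assumption. For count and concentration the change exists but is expected to be zero for 15.3 of 18 men at the 15% planning rate (12.6 at 30%, 9 at 50%), so linear regression is a poor choice.

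The risk of mislabelling is conditional. It needs an analyst to enter 0% for absent motility or morphology, and retinoid level to be related to response. Under assumed log-odds of 1.0 to 1.5 per SD, the zero-coded regression is significant in 21% to 46% of trials; with no link, in about 5%. The documents do not support saying that the plan calls for zero-coding, that the whole regression is void, or that the primary result is at risk. This is a supporting analysis whose outcome does not fit the design and should be restated before the data are analysed.

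**What to change.** Replace the regression sentence in section 14 with two statements:

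- (a) Baseline serum 13-cis retinoic acid, and its change to a named visit, are each related to sperm present at week 32 (yes/no) in all treated men, by an exact method with an estimate and 95% confidence interval. Label this exploratory. With 0 or 1 responders, give a description only. An exact rank-sum comparison or exact logistic regression would serve; name one in advance. Treat men without a week-32 sample as the primary analysis treats them.
- (b) Sperm count is reported for all men with a sample, with 0 for those without sperm. Motility and morphology are listed as on-treatment values only in men with sperm, with no change from baseline and no zero-coding.

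**Cost.** Two sentences, and no data beyond what the present sentence already needs. The trial gives up a formal linear-regression test of count, motility or morphology. The replacement is also weak: at 15% response with 18 men, there is a 22.4% chance of 0 or 1 responder and hence no usable exact test. The text should say so.
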